8.7.8 Incidence, Severity, and Duration of Organ Failure

The incidence, severity and duration of organ failure will be defined by the development of severe respiratory failure or severe renal failure or severe cardiac failure. Severe respiratory failure will be defined as those patients receiving invasive mechanical ventilation (IMV) or those receiving for ≥ 48 hours use of either high flow nasal cannula (HFNC) or non-invasive mechanical ventilation (NIMV). Use of IMV, HFNC, or NIMV for ventilatory support during a procedure, or use of NIMV for the treatment of obstructive sleep apnea, will not be considered as meeting the definition of severe respiratory failure. Severe renal failure will be defined as the initiation of renal replacement therapy. Severe cardiovascular failure will be defined as the use of vasopressor or inotropic support for ≥48 hours. Use of vasopressor or inotropic support during a procedure will not be considered as meeting the definition of severe cardiovascular failure.

The proportion and 95% CI of patients who developed severe respiratory failure or severe renal failure or severe cardiovascular failure will be displayed and analyzed in the same way as the rehospitalization for acute pancreatitis through Day 30. The proportion of and 95% CI of patients who developed more than one organ failure (multi-organ failure) will be also displayed and analyzed. The mean duration of severe respiratory failure, severe renal failure, and severe cardiac failure will be summarized by treatment groups.

Given the previous results from study CM4620-204, a sensitivity analysis that will combine the subjects from the 1.25 mL/kg and 0.625 mL/kg groups into one combined group and will combine the subjects from the 0.3125 mL/kg and placebo groups into another combined group. The proportion and 95% CI of patients who developed severe respiratory failure, as well as those who developed multiorgan failure, in the two combined groups will be displayed and analyzed in the same way as the re-hospitalization for acute pancreatitis through Day 30.

A gMCP-Mod analysis of severe respiratory failure will be conducted in the same three steps method as Session 8.6.1.

• Step 1: Conventional Step – Odds Ratio Between Each Dose Versus Placebo

The rate of severe respiratory failure will be analyzed using the logistic regression with treatment, sex (male or female) and the risk for organ failure (higher or lower) as covariates to obtain treatment effects and corresponding variance covariance matrix.

• Step 2: Candidate Models and Multiple Testing Procedure

Protocol CM4620-203 CONFIDENTIAL Page 22 of 31

The optimal contrast based on Candidate models for Auxora dose for the logit of rate of severe respiratory failure follows the following table

Model	Contrast coefficients for dose						
	Placebo	0.5 mg/kg	1.0 mg/kg	2.0 mg/kg			
Emax	0.866	-0.264	-0.293	-0.308			
sigEmax	0.663	0.300	-0.424	-0.539			

Note: Candidate model of Emax model is based on the assumption of parameter of ED50=0.026 mg/kg. Candidate model of sigEmax mode is based on the assumption of parameters of ED50=0.606 mg/kg and h=4.3

• Step 3: Dose-finding step – Dose-Response Model Fitting

The procedure is the same as the step 3 of Session 8.6.1.

The proportion and 95% CI of patients who developed new onset persistent respiratory failure or new onset persistent renal failure or new onset persistent cardiovascular failure will be displayed and analyzed in the same way as rehospitalization for acute pancreatitis through Day 30. New onset is defined as organ failure that was not present at randomization. Persistent is defined as ≥48 hours. Respiratory failure, renal failure, and cardiovascular failure are defined by a score of ≥2 on the modified Marshall scoring system. Patients with a known medical history of chronic kidney disease will be excluded from the analysis of new onset renal failure.

8.7.9 Mortality by Day 30

Mortality is recorded at the Day 30 follow-up assessment. The proportion and 95% CI of patients who died by Day 30 will be displayed and analysed in the same way as the re-hospitalization for acute pancreatitis through Day 30. If the Day 30 vital status is unknown and the patient has been discharged, the patient will be treated as alive.

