Appendix 1. Definition of Organ Failure and Sepsis

The definition of organ failure encompasses three organ systems, respiratory system, renal system and cardiovascular system.

For the respiratory system, organ failure will be defined as:

- PaO₂/FiO₂ ≤300 determined by arterial blood gas or imputed using pulse oximetry, or
- The use of high flow nasal cannula, non-invasive or invasive mechanical ventilation

For the renal system, in patients without known chronic kidney disease (baseline eGFR ≥60 mL/min/1.73 m²), organ failure will be defined as:

- An increase in serum creatinine ≥300% if the baseline creatinine is known from prior to the hospitalization for AP, or
- A serum creatinine ≥ 1.9 mg/dL, or
- The initiation of renal replacement therapy

For patients with pre-existing chronic kidney disease (baseline GFR <60 mL/min/1.73 m²), organ failure will be defined as:

- An increase in serum creatinine ≥300% if the baseline creatinine is known from prior to the hospitalization for AP, or
- An increase of serum creatinine to a level >4.0 mg/dl, or
- The initiation of renal replacement therapy

For the cardiovascular system, organ failure will be defined as:

- A systolic blood pressure <90 mmHg that is not fluid responsive, or
- The use of either vasopressor or inotropic support

Sepsis is the life-threatening organ dysfunction caused by a dysregulated host response to infection. For this study, organ dysfunction in the setting of infection will be defined by the presence of one of the following criteria:

- PaO₂/FiO₂ ≤300 determined by arterial blood gas or imputed using pulse oximetry
- The use of noninvasive or invasive mechanical ventilation
- Platelet count <100 x10³/uL
- Total bilirubin ≥2.0 mg/dL
- The use of vasopressor or inotropic support
- Serum creatinine ≥1.9 mg/dL in patients without pre-existing chronic kidney disease

- Serum creatinine >4.0 mg/dL in patients with pre-existing chronic kidney disease
- An increase in serum creatinine ≥300% if the baseline creatinine is known from prior to the hospitalization for acute pancreatitis
- The initiation of renal replacement therapy

Modified Marshall Scoring System: Organ Dysfunction in Acute Pancreatitis

		0 (None)	1 (None)	2 (Mild)	3 (Moderate)	4 (Severe)
Respiratory	PaO ₂ /FiO ₂	>400	301-400	201-300	101-200	≤100
Renal	Serum Cr mg/dL	<1.4	1.4-1.8	1.9-3.6	3.7-4.9	>4.9

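### SAP 8.7.8 has no rule for death before its 48-hour organ-failure thresholds, so an early death on vasopressors, high-flow oxygen or non-invasive ventilation is scored as no failure of that organ

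*SAP*

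**What the plan says.** SAP 8.7.8 covers the secondary endpoint of incidence, severity and duration of organ failure, and defines it through severe failure of three organs.

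- **Cardiovascular:** "Severe cardiovascular failure will be defined as the use of vasopressor or inotropic support for ≥48 hours".
- **Respiratory:** either invasive mechanical ventilation (IMV), with no minimum duration, or "those receiving for ≥ 48 hours use of either high flow nasal cannula (HFNC) or non-invasive mechanical ventilation (NIMV").
- **Renal:** "Severe renal failure will be defined as the initiation of renal replacement therapy", again with no minimum duration.

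Procedural use of respiratory or vasopressor support is excluded. A second analysis takes new-onset persistent failure, with failure of each organ set at a modified Marshall score of 2 or more: "New onset is defined as organ failure that was not present at randomization. Persistent is defined as ≥48 hours".

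The proportions are analysed as in SAP 8.7.4 (re-hospitalization). That section's only rule for missing status is that unknown becomes No. For duration, "The mean duration of severe respiratory failure, severe renal failure, and severe cardiac failure will be summarized by treatment groups". Neither 8.7.4 nor 8.7.8 says what to do when a patient dies before a threshold is reached.

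Protocol Appendix 1 sets no duration. Its cardiovascular definition includes "The use of either vasopressor or inotropic support", and any use of HFNC, NIMV or IMV meets the respiratory definition. SAP Table 4, which lists departures from the protocol, mentions only length of stay in the ICU.

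**The concern.** A minimum-duration rule works for patients who live long enough to meet or miss it. A patient who goes into shock and dies on vasopressors at 30 hours can do neither. Under the text that patient is a non-event for cardiovascular failure, scored the same as a patient weaned at 30 hours who went home. Two opposite outcomes share one code, and an arm with more early deaths on these supports shows a lower failure rate.

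The organ-failure results are compared between each dose and placebo. Severe respiratory failure also has its own gMCP-Mod dose-response analysis, and severe respiratory and multi-organ failure feed a pooled-dose sensitivity analysis. If events are few, which is an assumption, one or two misclassified patients matter.

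Duration has a related but separate problem: a plain mean treats support ended by death as support that was short.

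**Working it through.** **Inputs.** The definitions are those above. Group size is 54 (SAP 4). The documents give no organ-failure rate, early-death rate or power figure for this endpoint, so there is no plan figure to reproduce. All counts and durations below are assumptions.

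**Step 1. Apply the text to a patient who dies 24 hours after support starts.**

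| Support at death | Severe failure of that organ? | Enters mean duration? |
|---|---|---|
| Vasopressor or inotrope | No | No |
| HFNC or NIMV, never intubated | No | No |
| IMV (non-procedural) | Yes | Yes, about 1 day |
| Renal replacement | Yes | Yes, about 1 day |

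In the new-onset analysis, a patient who dies within 48 hours of onset scores No for that organ, whichever of the three it is.

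**Step 2. Size for incidence.** Let *f* patients per arm start a 48-hour support and all qualify except *d* in one arm who die before 48 hours. That arm is scored (*f* − *d*)/54 and the other *f*/54, so the gap is *d*/54.

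- With *f* = 5: 4/54 = 7.4%, 3/54 = 5.6% or 2/54 = 3.7% for *d* = 1, 2 or 3, against 5/54 = 9.3%.
- The gap depends only on *d*: 1/54 = 1.9 points to 3/54 = 5.6 points, for *f* from 3 to 8.
- If death on support counts as failure, both arms are *f*/54 and the gap is zero.

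**Step 3. Where it spreads.**

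- *Multi-organ failure* requires more than one organ. Losing one failure changes the count only if the patient has exactly one other qualifying organ failure.
- *The gMCP-Mod and the pooled comparison of severe respiratory failure* are affected only through HFNC or NIMV deaths, because vasopressors are not in that definition. Vasopressor deaths reach the pooled analysis only through multi-organ failure.
- *The Finkelstein-Schoenfeld and win-ratio composite* (SAP 8.9) compares respiratory failure only when both patients are alive at Day 30, so these patients are already settled on death.
- *Day 30 mortality* (SAP 8.7.9) does not use these definitions.

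**Step 4. Duration.** Take five patients on IMV, survivors ventilated 10 days and *m* dying on day 1. Mean = ((5 − *m*) × 10 + *m* × 1)/5, which is 10.0, 8.2, 6.4 and 4.6 days for *m* = 0, 1, 2 and 3. With survivors at 5 days it runs from 5.0 to 2.6; at 15 days, from 15.0 to 6.6. More deaths give a shorter mean.

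On days alive and free of support through Day 30, a survivor ventilated 10 days scores 30 − 10 = 20 and a death scores 0. The same cases average (5 − *m*) × 20/5 = 20, 16, 12 and 8, so the direction is right.

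**The case against.** The strongest defence is that the 48-hour line is not arbitrary. Protocol 1.1 describes the Atlanta classification, in which failure under 48 hours is transient and failure of 48 hours or more is persistent. Calling a 30-hour failure persistent because the patient died is a composite strategy, and the SAP uses a while-alive strategy itself in one length-of-stay analysis (8.7.3). Mortality is tested separately and ranked first in the composite, so readers will see the deaths, and duration is only summarised, not tested.

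Much of this stands, and it limits the reach of the point. It does not supply the missing rule. The SAP states how death is handled for length of stay (8.7.3) and for medically indicated discharge (8.7.2), but not in 8.7.8. Separate mortality reporting does not correct an organ-failure proportion read on its own.

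A reader might infer more than the documents support:

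- **That every organ failure must last 48 hours.** This is true of the new-onset persistent analysis but not of the severe definition, where IMV and renal replacement count at any non-procedural duration.
- **That one early death both erases the event and shortens the mean.** A death before 48 hours on vasopressors or HFNC/NIMV leaves the duration set. Shortening comes from deaths on IMV or renal replacement, or after 48 hours on the other supports.
- **That death after 36 hours on HFNC excludes persistent failure.** That analysis uses the Marshall score, which may have been 2 or more for longer than the HFNC was used.

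**Conclusion.** The point holds in a limited form. For vasopressors and inotropes, for HFNC or NIMV without intubation, and for new-onset persistent failure, the text scores death before 48 hours as absence of that failure. The direction is clear: it favours an arm with more such deaths. The size is unknown. The shift of 1.9 to 5.6 points rests on one to three such deaths in one arm of 54 and none in the other. Separately, mean duration shortens with death on support among patients who qualify.

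What is affected is the stand-alone organ-failure proportions, multi-organ failure on the condition in Step 3, the severe-respiratory gMCP-Mod and pooled comparison through HFNC/NIMV deaths only, and the duration summary. Neither mortality nor the composite is affected. This is a secondary-endpoint matter that should be settled in the SAP before unblinding.

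**What to change.** In SAP 8.7.8:

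1. State that a patient who dies while still receiving non-procedural vasopressor, inotrope, HFNC or NIMV support before 48 hours is counted as having that severe failure.
2. For new-onset persistent failure, count a patient who dies within 48 hours of onset with the failure unresolved, using only assessments from that interval. A rule based on the last Marshall score at any time would be unsafe: scheduled vital signs and SpO₂/FiO₂ stop at 240 hours and chemistries at 216 hours, and neither is scheduled for Days 12 to 28 (Protocol 8.8, 8.9, Appendix 8).
3. Report the literal 48-hour count as a sensitivity analysis.
4. Keep mean duration, labelled as a while-alive summary, because duration is a listed protocol endpoint (2.3). Add days alive and free of organ support through Day 30, with death by Day 30 scored 0.
5. Reconcile the 48-hour thresholds with Protocol Appendix 1, which has none, or list the change in SAP Table 4.

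The cost is SAP wording. Protocol 8.12.2 specifies administration times only for opioids, so the sponsor should confirm that start and stop times of support are captured; the existing 48-hour rule needs them anyway. The downside is slightly higher organ-failure counts and some overlap with mortality, which the sensitivity analysis makes visible.

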4. SAMPLE SIZE

A sample size of 216 patients will be randomized into four groups on a 1:1:1:1 basis, resulting in 54 patients randomized into each group. This sample size will provide 86% power for testing the difference in two populations having a median length of time of 72 and 144 hours, respectively, to tolerating solid food. This sample size will provide 80% power with a two-sided alpha of 0.05 to detect a 45% response rate for tolerating solid food in an Auxora dose group versus a 20% response rate in the placebo group in the 72 hours after completion of the first study drug infusion.

Protocol CM4620-203 CONFIDENTIAL Page 9 of 31

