The null hypothesis of flat dose-response relationship as compared to placebo for the primary efficacy endpoint will be tested at a significance level of one-sided 15% against the alternative hypothesis of a non-constant dose-response curve using a multiple contrast test as described in the gMCP-Mod methodology (Pinheiro et al., 2014). The contrast test statistic is a linear combination of the optimal contrast coefficients corresponding to the candidate dose-response curve with the hazard ratio at each individual dose obtained from Step 1 (conventional step).

The contrast coefficients are chosen to maximize the power to detect pre-specified candidate models. There are two candidate models that will be considered for the primary analysis with the optimal contrasts shown in following table. These optimal contrasts will be updated using the expected model means from the candidate set of the two models and the estimated variance-covariance matrix from the collected data. The updated contrast coefficients will be described in the final CSR.

The optimal contrast based on Candidate models for Auxora dose for log(Hazard Ratio):

Model	Contrast Coefficients for Dose					
Dose	0.5 mg/kg	1.0 mg/kg	2.0 mg/kg			
Emax	0.508	0.588	0.629			
sigEmax	-0.611	0.488	0.623			

Note: Candidate model of Emax model is based on the assumption of parameter of ED50=0.026 mg/kg. Candidate model of sigEmax mode is based on the assumption of parameters of ED50=0.707 mg/kg and h=6.34.

The proof of concept (PoC) is established if at least one dose-response model is statistically significant, thereby rejecting the null hypothesis of a flat dose-response curve and indicating a benefit of Auxora over placebo.

The global test decision is based on the maximum of the contrast test statistics. A critical value q controlling the type I error rate can be derived from the fact that the contrast test statistics approximately follow a multivariate normal distribution and that their maximum

Protocol CM4620-203 CONFIDENTIAL Page 15 of 31

follows the distribution of the maximum of a multivariate normal distribution. If the maximum contrast test statistic exceeds the critical value q, the overall null hypothesis of a flat dose-response curve is rejected, and one proceeds to characterize the dose-response efficacy relationship.

For each candidate dose-response curve, the test statistics and corresponding adjusted p-values will be presented.

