8.7.3 Length of Stay in the Hospital

The number of days patients are in the hospital from the SFISD, including ICU stay and readmissions for any etiology, during the 30 Days of the study will be summarized by treatment groups and compared between each Auxora treatment group and placebo group using an analysis of variance model, which includes treatment group, the stratification factor of the eCRF recorded sex (male or female), and then the stratification factor of the risk for organ failure (higher or lower) based on eCRF data as the fixed effects in the model. The proportion of patients in each quartile of hospital stay (1-7 days, 8-14 days, 15-21 days, and 22-30 days) and the patients who remain hospitalized at Day 30 will also be summarized by treatment groups.

Two sets of analyses will be conducted. The first analysis is to assess patient benefit; the number of days in the hospital will be defined as 30 if the patient dies due to acute pancreatitis (composite strategy). The second analysis is to assess healthcare systems benefit; the number of days in the hospital before the patient's death will be used in the analysis (while alive strategy).

8.7.4 Re-hospitalization for acute pancreatitis (AP) Through Day 30

The date of each re-hospitalization and the reasons for re-hospitalizations will be collected for each patient. The proportion and 95% CI of patients who are re-hospitalized for either acute pancreatitis or the development of pancreatic necrosis/necrotizing pancreatitis through the Day 30 visit will be displayed using a Clopper-Pearson interval and will be compared between each Auxora treatment group and placebo group using a Cochran-Mantel-Haenszel test stratified by the sex (male or female) and the risk for organ failure (higher or lower) based on eCRF data. Prohibited immunosuppressive medications or immunotherapies and treatment discontinuation will be ignored (treatment policy strategy). If the re-hospitalization for acute pancreatitis status is unknown, the re-hospitalization for acute pancreatitis will be imputed as No.

The proportion and 95% CI of patients who are re-hospitalized for other causes through Day 30 will also be analyzed in a similar manner.

Protocol CM4620-203 CONFIDENTIAL Page 20 of 31

8.7.5 Change in Severity of AP by CTSI Score from Screening to Day 30

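### The logistic fit feeding the severe respiratory failure gMCP-Mod test (SAP 8.7.8) breaks down when a dose arm has no events; pre-specify Firth regression and state which contrasts apply

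*SAP*

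**What the plan says.** SAP 8.7.8 states: "A gMCP-Mod analysis of severe respiratory failure will be conducted in the same three steps method as Session 8.6.1". In Step 1 the outcome "will be analyzed using the logistic regression with treatment, sex (male or female) and the risk for organ failure (higher or lower) as covariates". The stated purpose of this fit is "to obtain treatment effects and corresponding variance covariance matrix". That is ordinary maximum-likelihood logistic regression. Neither document mentions separation, an arm without events, or a penalised or exact fallback.

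Two rules for the contrasts are in play:
- 8.7.8 Step 2 says "The optimal contrast based on Candidate models for Auxora dose for the logit of rate of severe respiratory failure follows the following table" and prints fixed coefficients.
- 8.6.1, brought in by the reference to its three steps, also prints a table but adds: "These optimal contrasts will be updated using the expected model means from the candidate set of the two models and the estimated variance-covariance matrix".

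Within 8.7.8, only Step 3 points back to 8.6.1 by name. The test level also comes from 8.6.1, where the flat null "will be tested at a significance level of one-sided 15" percent.

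The same endpoint is also analysed by the method of 8.7.4, where proportions "will be compared between each Auxora treatment group and placebo group using a Cochran-Mantel-Haenszel test". On size, SAP 4 plans 216 patients, "resulting in 54 patients randomized into each group".

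**The concern.** The endpoint requires invasive ventilation, or at least 48 hours of high-flow or non-invasive support, so an arm of 54 could have no events. A treatment that works makes this more likely.

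The sigEmax candidate places most of the effect at the two higher doses. With ED50 0.606 and h 4.3, the fraction of maximum effect is 0.30 at 0.5 mg/kg, 0.90 at 1.0 and 0.99 at 2.0. The planned sensitivity analysis likewise pools the two higher doses against the lowest dose plus placebo. The arms most likely to be empty are therefore the ones that carry the signal.

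If an empty arm's variance explodes, the test discards or is swamped by its strongest evidence. Fewer events on active drug could turn a significant dose-response result into a null one and contradict the SAP's own CMH result on the same data. Where the contrast rule is open, the two readings can also give opposite answers.

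**Working it through.** **Inputs.** From the SAP: 54 per arm (section 4); one-sided 15% (8.6.1); the Step 1 model, printed contrasts, Emax ED50 0.026, and sigEmax ED50 0.606 with h 4.3 (8.7.8). Assumed, because the documents do not give them: event counts or rates, and the stratum mix.

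**1. The printed contrasts.** With equal arm variances the optimal contrast is the centred model mean scaled to unit length (sign reversed, as benefit lowers the rate).
- Emax: 0.866, -0.264, -0.293, -0.308, which matches exactly.
- sigEmax: 0.665, 0.296, -0.421, -0.540, against the printed 0.663, 0.300, -0.424, -0.539.

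The printed table is thus the equal-variance case, and the two rules differ once arm variances differ.

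**2. Chance of an empty arm.** (1 - p)^54 is 58% at a true rate of 1%, 34% at 2%, 11% at 4%, 6% at 5% and 1.1% at 8%. For at least one of two arms at 2%: 1 - (1 - 0.336)^2 = 56%.

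**3. Mechanism, by hand without covariates.** The logit variance is 1/y + 1/(54 - y).
- y = 6: logit ln(6/48) = -2.079, variance 0.1875.
- y = 1: logit ln(1/53) = -3.970, variance 1.019.
- y = 0: infinite.

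Printed sigEmax contrast at 6/6/1/1: 0.963 x (3.970 - 2.079) = 1.821. The variance is (0.663² + 0.300²) x 0.1875 + (0.424² + 0.539²) x 1.019 = 0.099 + 0.479 = 0.578, so z = 2.39.

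At 6/6/0/0, after 20 Newton steps, the empty arms have logit about -22.2 and SE about 9,000. Then z = 0.963 x (22.2 - 2.1) / (9,000 x 0.686) = 0.003.

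Without covariates, Firth adds half an event and half a non-event. An empty arm gets ln(0.5/54.5) = -4.69 with variance 1/[54 x (0.5/55) x (54.5/55)] = 2.056 (SE 1.43). A 6-event arm gets -2.01 with variance 0.178. Then z = 0.963 x 2.68 / sqrt(0.530 x 0.178 + 0.470 x 2.056) = 2.51.

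**4. Full model with sex and risk.** Strata of 19/8/19/8 per arm, six events placed 2/1/2/1. Entries are the largest z (critical value):

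| Events | Plain, updated | Plain, printed | Firth, updated | Firth, printed |
|---|---|---|---|---|
| 6/6/1/1 | 2.19 (1.28) | 2.40 (1.21) | 2.22 (1.28) | 2.36 (1.23) |
| 6/6/1/0 | 1.47 (1.26) | 0.00 (1.04) | 2.19 (1.27) | 2.39 (1.20) |
| 6/6/0/0 | 0.00 (1.04) | 0.00 (1.07) | 2.17 (1.27) | 2.58 (1.18) |
| 6/0/0/0 | 0.00 (1.18) | 0.00 (1.33) | 3.02 (1.19) | 3.01 (1.32) |

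At 6/6/0/0 the updated contrasts from the plain fit become (0.707, -0.707, 0, 0). The two informative arms are dropped, and two arms with equal counts are compared.

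CMH there, each higher dose against placebo: observed 6, expected 3, variance 2 x (0.25 x 2 x 36/37) + 2 x 0.25 = 1.473. Chi-square = 9/1.473 = 6.11, p = 0.013. The pooled-dose CMH gives p = 0.0004.

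**5. Power at assumed rates.** 2,000 trials each; 50% per sex, 30% higher risk, no covariate effects; Monte Carlo error about 1 point. Power columns show plain vs Firth:

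| True rates % | A dose arm empty | Updated | Printed |
|---|---|---|---|
| 10/10/2/2 | 56% | 58% vs 81% | 37% vs 90% |
| 12/12/4/4 | 22% | 67% vs 75% | 63% vs 82% |
| 10/8/4/4 | 21% | 53% vs 57% | 50% vs 65% |
| 15/15/6/6 | 6% | 75% vs 75% | 77% vs 81% |
| 20/20/8/8 | 2% | 86% vs 86% | 88% vs 90% |

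Repeat runs of the top row gave 55% to 60% against 80% to 81% with updated contrasts. A separate simulation at 10/8/2/2% used 20% higher risk, 35% in one sex, risk odds ratio 4 and sex odds ratio 0.8. It gave 61% vs 79% updated and 35% vs 87% printed; with printed contrasts the plain fit never rejected when a dose arm was empty.

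**6. False positives under flat rates of 2% to 10% (nominal 15%).** Firth: 8% to 12% updated, 11% to 17% printed. The separate simulation gave 6.6% to 11.4% and 10.3% to 15.7%. The plain fit also reached 17% with printed contrasts at a flat 10%.

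**The case against.** The strongest reply has four parts.

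- **Reading.** 8.7.8 adopts the three steps of 8.6.1, so the natural reading is that contrasts are updated, and the worst printed-contrast figures then fall away. This is a fair reading, but 8.7.8 Step 2 refers only to its own table, so the rule needs stating. Updating does not rescue 6/6/0/0 or 6/0/0/0.
- **One empty arm need not be fatal.** With updated contrasts the plain fit still rejects at 6/6/1/0 (1.47 against 1.26) and at 6/5/2/0 (1.38 against 1.26). This stands: outright failure needs every arm carrying the effect to be empty. Power is still lost short of that.
- **Reach.** This is one model for one component of a secondary endpoint. The CMH tests, pooled comparison, composite and Cox-based primary analysis do not use it, and dose selection rests on the totality of the data. With updated contrasts the gain is small once active-arm rates reach 4% and about nil at the highest rates tried. This also stands, and it limits the importance of the point.
- **Firth is one choice among several and is not better calibrated.** With updated contrasts at flat 2%, 5% and 10%, one comparison of 1,000 trials each gave 5%, 10% and 10% for the plain fit and 9%, 12% and 9% for Firth. Both are conservative. The case for Firth is power and a finite answer, not calibration.

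**Conclusion.** The concern holds. Followed exactly, Step 1 can return z near zero because the drug worked better. The non-result is partly an artefact of when the software stops: at 6/5/2/0 the empty arm's SE was 30 after 8 iterations and about 149,000 after 25.

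The fixed-count results need no assumed event rate, only an assumed spread over strata. The power loss does depend on unstated rates: with updated contrasts, about 23 points at 10/10/2/2%, 4 to 8 points at active rates of 4%, and none at placebo rates of 15% or more. All results assume that the 15% level of 8.6.1 carries over. Confidence in the mechanism is high; the practical impact is conditional and confined to this secondary analysis. The change should be made because it is cheap and avoids choosing a method after unblinding.

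**What to change.** In SAP 8.7.8:

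1. In Step 1, specify Firth-penalised logistic regression (the FIRTH option in PROC LOGISTIC) with the same covariates, and carry its estimates and covariance into Steps 2 and 3.
2. In Step 2, state whether the printed or the updated contrasts apply. Updating with the Firth covariance is consistent with 8.6.1 and kept false positives below the nominal 15% in every flat scenario tried; printed contrasts reached 17%.

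The cost is one option in the SAS code and two sentences. The downside is slight shrinkage of the odds ratios toward 1.
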